## 3. Abstract:

At the Malcom Randall Veterans Affairs Medical Center (MRVAMC), intra-cardiac pressures are routinely recorded after transcatheter aortic valve replacement (TAVR) procedures. Our research has disclosed that patients with abnormal hemodynamics (narrow aortic to ventricular end-diastolic pressure difference, indexed to heart rate) suffer from high long-term mortality, compared with patients with normal hemodynamics. Hypertension and diastolic dysfunction are highly co-morbid conditions among these patients. The selective aldosterone receptor antagonist eplerenone (Inspra) is approved for use in the treatment of hypertension. Research also supports that eplerenone may be able to improve diastolic function.

This prospective registry is interested in determining 1) the tolerability of eplerenone, and 2) feasibility of administering the Kansas City Cardiomyopathy Questionnaire (KCCQ) among patients with abnormal hemodynamics after TAVR. This registry will set the stage for a pilot randomized trial to evaluate eplerenone versus placebo among patients with abnormal hemodynamics after TAVR.

## 4. Background:

Our research has disclosed that patients who have abnormal hemodynamics (narrow aortic to ventricular end-diastolic pressure difference, indexed to heart rate) after TAVR suffer from poor long-term survival. This hemodynamic value can be referred to as the aortoventricular index (AVi). In a single center observational study, the 2-year mortality rate for patient with a value  $\geq 0.6$  mm Hg/bpm was 25% compared with 36% for patients with a value  $< 0.6$  mm Hg/bpm. An abnormal AVi was an independent predictor for poor survival. Hypertension and diastolic dysfunction are 2 highly co-morbid conditions among these patients. Currently, there is lack of appreciation that pressure measurements obtained at the time of TAVR can provide long-term prognostic value. There is also a lack of understanding on how to improve outcomes and quality of life among such patients.

Eplerenone is a selective aldosterone receptor antagonist approved for use for treatment of hypertension. Animal studies have shown that aldosterone receptor antagonists can decrease interstitial myocardial fibrosis. The non-selective aldosterone receptor antagonist, spironolactone 25 mg daily compared with placebo was shown to improve diastolic function, as assessed by echocardiography, among 28 elderly

subjects. A meta-analysis of eleven studies in 942 subjects found that aldosterone receptor antagonists improve diastolic function and markers of cardiac fibrosis without significant changes to left ventricular mass or dimensions. In a randomized controlled trial, eplerenone was found to be safely tolerated among asymptomatic patients with moderate to severe aortic stenosis.

The purpose of this registry is to set the stage for a pilot randomized trial to test our ultimate hypothesis that eplerenone versus placebo can improve survival and quality of life among TAVR patients documented to have abnormal hemodynamics. The KCCQ is a validated research tool to measure health status (physical limitation, symptom frequency, quality of life, and social limitation) among patients with aortic stenosis and heart failure symptoms.

## **5. Specific Aims:**

- 1) Determine the tolerability of eplerenone among patients with abnormal hemodynamics and hypertension after TAVR.
- 2) Determine the feasibility of administering the KCCQ-12 at baseline and 8 weeks to assess quality of life.

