## **6. Research Plan:**

- 1) Enroll 25 subjects with hypertension and abnormal hemodynamics after TAVR.
- 2) Enrollment for non-local subjects will occur remotely with telephonic consent and mailing of the questionnaire and study drug. Enrollment for local subjects will occur remotely or in-person.
- 3) This is a greater than minimal risk study.
  - a. Inclusion criteria:
    - i. TAVR procedure performed at the Malcom Randall VA Medical Center within the last 2 years.
    - ii. Intracardiac pressures recorded 5 to 10 minutes after TAVR and AVi < 0.6 mm Hg/bpm.
    - iii. History of hypertension, taking anti-hypertensive medications, or recent systolic blood pressure  $\geq$ 130 mm Hg.
  - b. Exclusion criteria:
    - i. Serum potassium >5.5 mEq/L at initiation.
    - ii. Concomitant administration of strong CYP3A inhibitor (i.e. ketoconazole, itraconazole, nefazodone, troleandomycin, clarithromycin, ritonavir, and nelfinavir).
    - iii. Serum creatinine >2.0 for men and >1.8 for women.
    - iv. Creatinine clearance <50 cc/min.
    - v. Concomitant administration of potassium supplements or potassium-sparing diuretics.

- 4) Subjects who are eligible to participate and signed an informed consent will be given eplerenone 50 mg daily. Study drug (eplerenone) will be paid by the North Florida Foundation for Research and Education for the duration of the study.
  - a. Down-titration or termination of non-essential anti-hypertensive agents is permissible so that eplerenone does not result in hypotension. Essential medications are as follows:
    - i. Angiotensin converting enzyme inhibitors (ACE-inhibitors) or angiotensin receptor blockers, if intolerant to ACE-inhibitors are indicated for treatment left ventricular dysfunction (i.e. left ventricular ejection fraction  $\leq 40\%$ ), diabetes, and proteinuric chronic kidney disease.
    - ii. Beta-blockers are indicated 3 years after an acute myocardial infarction, unless there is persistent left ventricular dysfunction (i.e. left ventricular ejection fraction  $\leq 40\%$ ).
- 5) Monitoring.
  - a. Serum potassium within the last 30 days is required before initiating eplerenone. Repeat blood draw is required within the first week, and one month after the start of treatment with eplerenone.
  - b. An order will be placed for the blood draws to be performed at the subject's local VA community-based outpatient clinic or hospital.

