5/14/2020

NCT03923530

IRB 201901097

Pressure Assessment to Improve Outcomes after TAVR:
a registry

IRB 201901097

Pressure Assessment to Improve Outcomes after TAVR: a registry

5/14/2020

NCT03923530

- 1.
2. We used Kolmogorov-Smirnov and Shapiro-wilk tests to examine distribution of our data. Despite small sample size, we had normal distribution. Therefore, we used parametrical approaches to compare means before and after the TAVR.
3. We used descriptive analysis to calculate Mean and standard deviation for age of the patients.
4. We used paired t-test to compare mean Kansas City Cardiomyopathy Questionnaire parameters, including physical limitation, symptom frequency, quality of life, social limitation, and overall summary before and after TAVR. We employed the paired t-test to compare mean of left ventricular end diastolic pressure, systolic and diastolic blood pressures before and after TAVR as well.
5. P value less than 0.05 was considered as statistically significant.
6. All statistics were done by SPSS software, version 24 (IBM Corp., Armonk, NY, USA).

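### The readable SAP items (2 to 6; item 1 is blank in the text available) contain no analysis of either stated aim: eplerenone tolerability or KCCQ-12 feasibility

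*Protocol*

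**What the plan says.** Protocol section 5 gives two aims. The first is to "Determine the tolerability of eplerenone among patients with abnormal hemodynamics and hypertension after TAVR". The second is to "Determine the feasibility of administering the KCCQ-12 at baseline and 8 weeks to assess quality of life". The Abstract (section 3) names the same two, and the Abstract and Background (section 4) say that the registry prepares for a randomised pilot of eplerenone against placebo.

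Section 6 sets the size, "Enroll 25 subjects with hypertension and abnormal hemodynamics after TAVR", and schedules data that bear on both aims:
- potassium before treatment, in the first week and at one month (item 5a);
- a coordinator's call at 8 weeks on vital status and adverse reactions (item 6a);
- the KCCQ-12 at baseline and 8 weeks, mailed to every subject (item 6a);
- blood pressure at 8 weeks (item 5c).

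The SAP is a list of six items. Item 1 carries a number and no text. Item 2 tests normality and reports the outcome: "Despite small sample size, we had normal distribution". Item 3 reads "We used descriptive analysis to calculate Mean and standard deviation for age of the patients". Item 4 begins "We used paired t-test to compare mean Kansas City Cardiomyopathy Questionnaire parameters" and adds a paired t-test to "compare mean of left ventricular end diastolic pressure, systolic and diastolic blood pressures before and after TAVR as well". Item 5 sets the threshold at P below 0.05, and item 6 names the software.

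**The concern.** The registry asks whether patients can take the drug and whether the questionnaire can be administered. Both answers are counts of subjects. The readable SAP offers comparisons of means instead, framed around the valve procedure rather than eplerenone.

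The planners of the randomised pilot need to know how many subjects did not tolerate eplerenone, what happened to potassium, and how many subjects returned a usable KCCQ-12 at both times. A significant or non-significant mean change in KCCQ score, LVEDP or blood pressure supplies none of these. The registry could complete its analysis as written and still leave both of its own questions open.

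**Working it through.** **1. Aims against SAP items.** The SAP states no power, precision or success figure to reproduce, so the check is a comparison of texts.

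| SAP item | Content | Tolerability (aim 1) | Feasibility (aim 2) |
|---|---|---|---|
| 1 | No text available | unknown | unknown |
| 2 | Normality tests | no | no |
| 3 | Mean and SD of age | no | no |
| 4 | Paired t-tests | no | no |
| 5 | 0.05 threshold | no | no |
| 6 | Software | no | no |

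Of the five readable items, 0 analyse aim 1 and 0 analyse aim 2. None mentions eplerenone, adverse reactions, potassium, vital status, questionnaire return or the 8-week visit. No section of the protocol fills the gap.

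**2. Whether item 4 could serve indirectly.** It holds 5 (KCCQ scores) + 1 (LVEDP) + 2 (systolic and diastolic pressure) = 8 paired tests.

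- *Label.* Inclusion criterion i requires TAVR to have been done already, within the previous 2 years. The study's KCCQ-12 baseline therefore falls after TAVR. A comparison of values either side of the procedure is not the contrast that section 6 sets up, which is study baseline against 8 weeks on eplerenone.
- *KCCQ.* Aim 2 mentions quality of life, so mean scores have a place. But a paired test uses only subjects with both scores. Those lacking one are the subjects a feasibility analysis has to count, and the test does not report them.
- *Blood pressure.* It could bear on tolerability through hypotension. Section 6 schedules a study reading only at 8 weeks. Item 4a of that section also allows non-essential anti-hypertensive agents to be reduced or stopped, so a mean change would mix that influence with eplerenone's. It would not count intolerant subjects either.
- *LVEDP.* The only intracardiac reading in section 6 is the entry measurement shortly after TAVR (inclusion criterion ii), which precedes eplerenone. No repeat is scheduled.

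**3. What an aim-matched analysis would deliver at n = 25.** The counts are assumed. The formula is the two-sided exact (Clopper-Pearson) 95% interval: lower limit = 0.025 quantile of Beta(x, n − x + 1); upper limit = 0.975 quantile of Beta(x + 1, n − x).

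- Intolerance in 0 of 25: upper limit = 1 − 0.025^(1/25) = 13.7%.
- KCCQ-12 complete at both times in 20 of 25: lower limit = 0.025 quantile of Beta(20, 6) = 59.3%; upper limit = 0.975 quantile of Beta(21, 5) = 93.2%.

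In the second example the KCCQ t-tests would rest on 20 pairs, and 25 − 20 = 5 subjects would be absent from them.

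**The case against.** The strongest objection is that one of the six SAP items cannot be read, and it is the first, where endpoints could sit. Text lost in extraction is not missing from the plan. This stands. A reader might infer that the whole SAP ignores the aims, but the documents support that only for items 2 to 6.

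A reader might also infer that subjects who do not complete the questionnaire disappear from the analysis altogether. They do not. The age summary and the blood pressure and LVEDP tests need no KCCQ form, so these subjects may still appear there. They drop out only of the KCCQ tests. If the number of pairs or the degrees of freedom were reported, the number with both scores could be recovered. That is an indirect route to completion, and the SAP does not commit to reporting either figure.

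A third tempting inference is that the blood pressure and LVEDP comparisons cannot be made at all. Section 6 shows only what the study schedules. Inclusion criterion iii refers to a recent systolic pressure, which as one of several alternatives does not guarantee a value for everyone, and the Abstract says that intracardiac pressures are routinely recorded after TAVR at this centre. Clinical records may hold further values.

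Finally, plain counts would answer both aims in a single-arm registry of 25. Exact intervals add a statement of precision but are not what is missing. Scoring a death as an uncompleted questionnaire would also merge mortality with feasibility, so deaths are better shown on their own line.

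**Conclusion.** The point holds for the readable SAP: 0 of 2 aims has an analysis in items 2 to 6. Item 4 is no substitute, because it tests mean changes under a time label that does not fit a study enrolling after TAVR. This goes beyond missing detail, since carrying out the readable plan would not answer the questions for which the registry was set up.

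Confidence is moderate, because item 1 is unread and the conclusion must be revised if it holds an aim-related analysis. The intervals rest on assumed counts and show only the precision available at 25 subjects; the omission does not depend on them. The documents do not show that the relevant data went uncollected. Section 6 schedules most of what is needed.

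**What to change.** Amend the SAP so that the main analyses are:

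1. **Tolerability:** number and proportion of treated subjects with an intolerance event by 8 weeks. The sponsor defines the event, using the adverse reactions collected at the 8-week call. List deaths and unknown status separately.
2. **Potassium:** summary at baseline, first week and one month, with the number of draws obtained at each time.
3. **Feasibility:** number and proportion of enrolled subjects with an evaluable KCCQ-12 at both baseline and 8 weeks, with deaths and non-returns shown separately.

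Give exact 95% intervals for the proportions.

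For item 4, make the KCCQ comparison secondary. Relabel it baseline versus 8 weeks if that is what was compared, and print the number of pairs beside the number enrolled. For blood pressure and LVEDP, state when each value was taken and whether it came from clinical records.

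The SAP is written in the past tense and already reports a distributional result, so label the additions post hoc if the data have been examined. If item 1 contains any of these analyses, restore its text.

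The cost is a SAP amendment, a sponsor definition of intolerance and three short tables. The potassium and KCCQ-12 tables use data the protocol already schedules. The intervals will be wide at 25 subjects.

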## **6. Research Plan:**

- 1) Enroll 25 subjects with hypertension and abnormal hemodynamics after TAVR.
- 2) Enrollment for non-local subjects will occur remotely with telephonic consent and mailing of the questionnaire and study drug. Enrollment for local subjects will occur remotely or in-person.
- 3) This is a greater than minimal risk study.
  - a. Inclusion criteria:
    - i. TAVR procedure performed at the Malcom Randall VA Medical Center within the last 2 years.
    - ii. Intracardiac pressures recorded 5 to 10 minutes after TAVR and AVi < 0.6 mm Hg/bpm.
    - iii. History of hypertension, taking anti-hypertensive medications, or recent systolic blood pressure  $\geq$ 130 mm Hg.
  - b. Exclusion criteria:
    - i. Serum potassium >5.5 mEq/L at initiation.
    - ii. Concomitant administration of strong CYP3A inhibitor (i.e. ketoconazole, itraconazole, nefazodone, troleandomycin, clarithromycin, ritonavir, and nelfinavir).
    - iii. Serum creatinine >2.0 for men and >1.8 for women.
    - iv. Creatinine clearance <50 cc/min.
    - v. Concomitant administration of potassium supplements or potassium-sparing diuretics.

- 4) Subjects who are eligible to participate and signed an informed consent will be given eplerenone 50 mg daily. Study drug (eplerenone) will be paid by the North Florida Foundation for Research and Education for the duration of the study.
  - a. Down-titration or termination of non-essential anti-hypertensive agents is permissible so that eplerenone does not result in hypotension. Essential medications are as follows:
    - i. Angiotensin converting enzyme inhibitors (ACE-inhibitors) or angiotensin receptor blockers, if intolerant to ACE-inhibitors are indicated for treatment left ventricular dysfunction (i.e. left ventricular ejection fraction  $\leq 40\%$ ), diabetes, and proteinuric chronic kidney disease.
    - ii. Beta-blockers are indicated 3 years after an acute myocardial infarction, unless there is persistent left ventricular dysfunction (i.e. left ventricular ejection fraction  $\leq 40\%$ ).
- 5) Monitoring.
  - a. Serum potassium within the last 30 days is required before initiating eplerenone. Repeat blood draw is required within the first week, and one month after the start of treatment with eplerenone.
  - b. An order will be placed for the blood draws to be performed at the subject's local VA community-based outpatient clinic or hospital.
  - c. Blood pressure will be recorded in the research office for local subjects and through the primary care provider for non-local subjects at 8 weeks.
- 6) Quality of life questionnaire.
  - a. The Kansas City Cardiomyopathy Questionnaire (KCCQ-12) will be administered at baseline and 8 weeks. The KCCQ-12 instrument will be mailed to all subjects. Local subjects will be given the opportunity to complete the questionnaire in the research office, if they prefer. Study coordinator will call the subject at 8 weeks to confirm vital status, assess if any adverse reactions from eplerenone, and provide assistance to completing the KCCQ-12, if needed.

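### Read literally, the only beta-blocker entry in the essential-medications list removes protection at ejection fraction ≤40%; secondarily, no record of background drug changes is specified

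*Protocol*

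**What the plan says.** Protocol section 6, item 4, starts every subject on eplerenone 50 mg daily. Item 4a then gives a permission: "Down-titration or termination of non-essential anti-hypertensive agents is permissible so that eplerenone does not result in hypotension". A two-entry list of essential drugs limits that permission.

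- Item 4a.i covers ACE inhibitors, or angiotensin receptor blockers when an ACE inhibitor is not tolerated. These "are indicated for treatment left ventricular dysfunction" (ejection fraction 40% or lower is given as the example), and also for diabetes and proteinuric kidney disease.
- Item 4a.ii covers beta-blockers: "Beta-blockers are indicated 3 years after an acute myocardial infarction, unless there is persistent left ventricular dysfunction". The same ejection fraction example follows.

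The first aim in section 5 is: "Determine the tolerability of eplerenone among patients with abnormal hemodynamics and hypertension after TAVR". There is one treated group and no control arm.

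Follow-up is set out in section 6, items 5 and 6. For blood tests: "Repeat blood draw is required within the first week, and one month after the start of treatment with eplerenone". Blood pressure is taken at 8 weeks, in the research office for local subjects and "through the primary care provider for non-local subjects at 8 weeks". For adverse reactions: "Study coordinator will call the subject at 8 weeks to confirm vital status, assess if any adverse reactions from eplerenone". The same call offers help with the KCCQ-12.

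**The concern.** Item 4a works as a stop-or-keep rule: whatever the list does not protect may be reduced or stopped. Its wording should therefore allow one reading only. In ordinary grammar, *unless* introduces an exception, so item 4a.ii says the beta-blocker indication does not hold when ventricular dysfunction persists. A reader who follows the sentence as written could withdraw a beta-blocker from the patients it was probably meant to protect. This is a patient-safety matter in a study that rates itself above minimal risk.

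A secondary matter is independent of how item 4a.ii is worded. With no control arm, a symptom that follows withdrawal of a background drug can be taken for a reaction to eplerenone. Equally, cutting a background drug can offset a fall in blood pressure on eplerenone. A reader of the tolerability results would need to know who had such a change, and the documents do not call for that information.

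**Working it through.** The plan gives no figure on this point, so there is nothing to reproduce. The check has three steps.

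**1. Does anything else in the documents settle the meaning?** Item 4a.ii is the only statement on beta-blockers in either document. Two features point to the likely intent. *Persistent* fits a limit on duration that is being extended, and item 4a.i, directly above, uses the same ejection fraction threshold as a reason for keeping a drug. The five exclusion criteria concern potassium level, strong CYP3A inhibitors, serum creatinine, creatinine clearance, and potassium-sparing diuretics or supplements. None removes prior infarction or low ejection fraction, so the affected patients can be enrolled.

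**2. What does each reading do?** Take beta-blocker users with a prior infarction. Let T mean infarction at most 3 years ago and L mean ejection fraction at most 40%. Y means essential (protected); N means it may be stopped.

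| Reading of item 4a.ii | Rule | T, L | T, not L | not T, L | not T, not L | Differs from likely intent |
|---|---|---|---|---|---|---|
| 1. Up to 3 years; *unless* extends (likely intent) | T or L | Y | Y | Y | N | 0 of 4 |
| 2. Up to 3 years; *unless* cancels (literal) | T and not L | N | Y | N | N | 2 of 4 |
| 3. From 3 years on; *unless* extends | not T, or L | Y | N | Y | Y | 2 of 4 |
| 4. From 3 years on; *unless* cancels | not T and not L | N | N | N | Y | 4 of 4 |

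Readings 1 and 2 give opposite instructions in both columns with L, and agree elsewhere. Readings 3 and 4 arise because the time phrase does not say whether it means up to or from 3 years. They are less likely, and reading 4 needs two unlikely choices at once. The replacement wording proposed below gives Y, Y, Y, N, the same as reading 1. The columns are types of patient and carry no information on how many subjects fall in each.

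The entry also leaves one case open: low ejection fraction without a previous infarction.

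**3. What is to be recorded?**

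| Item specified | When | Covers changes in background drugs? |
|---|---|---|
| Serum potassium / blood draw | Baseline, first week, one month | No |
| Blood pressure | 8 weeks | No |
| KCCQ-12 | Baseline, 8 weeks | No |
| Coordinator call: vital status, adverse reactions, questionnaire help | 8 weeks | No |

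The SAP has no summary or listing of concomitant drugs.

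**The case against.** On the wording, the strongest reply is that a clinician would understand what is meant. The document's own cues favour reading 1, under which nothing changes (0 of 4 types). Item 4a only permits stopping a drug and never requires it, and the number of patients concerned may be zero. All of this stands and limits the weight of the point. It does not remove it: the literal reading is grammatically available, it runs against item 4a.i, and a safety rule should not depend on its readers correcting it.

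A reader might infer that the protocol intends beta-blockers to be withdrawn at low ejection fraction. The documents do not support that; the fault is in the sentence.

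On recording, the reply is that silence in the plan does not show that changes go unrecorded. Clinic records may hold them, and the starting regimen has to be looked at to apply the criteria on anti-hypertensives, CYP3A inhibitors and potassium-raising drugs. Reducing background drugs is also part of the design, since item 4a allows it in order to avoid hypotension. What is assessed is eplerenone with background adjustment. This stands too. A reader might infer that the tolerability results are biased by a known amount, but the documents give no count of drug changes or of reactions from which to work out any such amount.

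**Conclusion.** The main point holds as a wording fault in an operative safety rule. Literally read, item 4a.ii leaves beta-blockers unprotected at ejection fraction ≤40%, contrary to item 4a.i and to the likely intent. The difference is 2 of 4 patient types under the literal reading and none under the likely one. The conclusion rests on the text alone, with intent inferred from *persistent* and from item 4a.i. The number of subjects affected is unknown and may be zero.

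The recording point is secondary. It holds only in this form: the documents specify no record of background anti-hypertensives reduced or stopped under item 4a, although the first aim is tolerability without a control arm. It supports a descriptive addition and does not show that any result is wrong. It does not depend on the SAP's blood pressure comparison before and after TAVR.

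**What to change.** Replace item 4a.ii with: *Beta-blockers are essential for up to 3 years following an acute myocardial infarction, and beyond 3 years if left ventricular ejection fraction remains ≤40%.* The sponsor's clinicians should confirm that this is the intended rule and state whether ejection fraction ≤40% without infarction also makes the drug essential.

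For the secondary point, list anti-hypertensive drugs and doses at baseline. Note any change (drug, dose, date, reason) at the existing 8-week contact or from the clinic record. For non-local subjects, the primary care provider who already supplies the blood pressure can be asked. Show the changes beside adverse reactions and 8-week blood pressure, as a listing without a test.

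The cost is one protocol sentence, a little extra data entry and one listing, with no added visits. Recall at 8 weeks may miss small dose changes, which is why the baseline list and the clinic record matter. Because drugs are reduced to avoid hypotension, the listing can show timing but cannot prove cause. The SAP is written in the past tense; if follow-up was already complete, the reworded rule would come too late for these subjects and the drug changes could be recovered only from records. Both changes would still be worth carrying into the planned pilot randomized trial.

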### **Study medication:**

Eplerenone is a Food and Drug Administration approved medication for treatment of hypertension. Eplerenone was documented to be safely tolerated among patients with moderate to severe asymptomatic aortic stenosis. This medication can increase serum

potassium which will be monitored at baseline, 1 week and 4 weeks after initiation. Possible adverse reactions include: headache, dizziness, diarrhea, stomach pain, chest pain, nausea, cough or flu-like symptoms (such as fever, chills, body aches, or unusual tiredness), vaginal bleeding, breast swelling/tenderness, or rash.

**Questionnaire:** Possible emotional discomfort when answering some of the questions; however, this risk is exceeding small.

**Confidentiality:** Confidential information about subjects might be accidentally disclosed. We will use our best efforts to keep the protected health information secure. The risk of accidental disclosure is exceeding small.

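### Symptomatic reactions to eplerenone are actively asked about only once, at 8 weeks and only as drug reactions, with no matching baseline, so symptomatic intolerance may be mis-estimated in either direction.

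*Protocol*

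**What the plan says.** Specific Aim 1 of the protocol is: "Determine the tolerability of eplerenone among patients with abnormal hemodynamics and hypertension after TAVR". Tolerability is not defined further.

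The Research Plan places the enquiry about reactions under the quality-of-life item (6a), not under Monitoring: "Study coordinator will call the subject at 8 weeks to confirm vital status, assess if any adverse reactions from eplerenone". No other scheduled symptom enquiry is described. Nor is an adverse-event log, a rule for causality, or a record of whether and why a subject stopped the drug.

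Other safety data are planned. On laboratory tests, item 5a says: "Repeat blood draw is required within the first week, and one month after the start of treatment with eplerenone". Section 7 (Study medication) makes clear that these draws serve "potassium which will be monitored at baseline, 1 week and 4 weeks after initiation". Item 5b says who does them: "An order will be placed for the blood draws to be performed at the subject's local VA community-based outpatient clinic or hospital". Item 5c adds: "Blood pressure will be recorded in the research office for local subjects and through the primary care provider for non-local subjects at 8 weeks".

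Section 7 also lists what might be expected: "Possible adverse reactions include: headache, dizziness, diarrhea, stomach pain, chest pain, nausea", followed by other complaints that are mostly symptoms too. The SAP tests KCCQ scores, left ventricular end-diastolic pressure and blood pressure. It has no analysis of reactions, potassium or stopping of the drug.

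**The concern.** Most of the reactions in section 7 come to light only if the subject reports them or someone asks. One enquiry at 8 weeks depends on memory for anything that came and went in the first weeks. Limiting it to reactions caused by the drug means that attribution is decided before anything is recorded. Without the same questions before the first dose, a complaint such as headache or dizziness at 8 weeks cannot be classed as new or old.

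The registry is meant to prepare a randomized pilot, and its tolerability result is one of two things it hands on. Non-local subjects are consented by telephone and sent the drug by post, so no study visit is described at which they would mention a symptom in passing.

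**Working it through.** The documents give no expected intolerance rate, capture rate, precision target or derivation of the sample size, so there is no planned figure to reproduce. The one documented input is N = 25 ("Enroll 25 subjects with hypertension and abnormal hemodynamics after TAVR"). The rates below are assumptions, chosen to show a range.

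**1. What is collected, and when**
- Before treatment: potassium and KCCQ-12. No enquiry about the section 7 list.
- Within week 1: potassium, drawn at a local VA site.
- One month: potassium, drawn at a local VA site.
- 8 weeks: blood pressure, KCCQ-12, and the coordinator's call about reactions.

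Symptoms other than those in the KCCQ-12 therefore have one scheduled time point and no baseline.

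**2. Missed reactions**

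Let p be the true proportion with symptomatic intolerance and s the fraction of those subjects whose reaction is recorded. The recorded proportion is p × s, and the chance of recording no case in 25 is (1 − p × s)^25.
- p = 20%: full capture gives 5.0 expected cases; s = 0.8 gives 16% (4.0 cases); s = 0.5 gives 10% (2.5 cases). The chance of no case is 0.4%, 1.3% and 7.2% respectively.
- p = 10%: expected cases are 2.5, 2.0 and 1.25. The chance of no case is 7.2%, 12.4% and 27.7%.

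**3. Wrongly attributed complaints**

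Let f be the proportion of subjects without true intolerance who are nevertheless recorded as having a reaction. The recorded proportion becomes p × s + (1 − p) × f. It equals p when f = p(1 − s)/(1 − p).
- p = 20%, s = 0.8: f = 0.04/0.80 = 5%, that is 1 of the other 20 subjects.
- p = 20%, s = 0.5: f = 0.10/0.80 = 12.5%.
- p = 10%, s = 0.5: f = 0.05/0.90 = 5.6%.

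Above these values the rate is over-stated. With p = 20%, s = 0.8 and f = 12.5%, for example, the recorded rate is 0.16 + 0.10 = 26%.

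**4. Sampling error for comparison**

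Exact (Clopper-Pearson) 95% intervals with 25 subjects are 0% to 13.7% for 0/25, 2.5% to 31.2% for 3/25, and 6.8% to 40.7% for 5/25. They cover chance only and correct for neither error above.

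**5. Subjects who cannot answer**

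The Background gives 36% two-year mortality for patients with a low index. With a constant hazard, the 8-week risk is 1 − (1 − 0.36)^(56/730) = 3.4%, and 25 × 0.034 is about 0.84 deaths. This is rough: the 36% is two-year post-TAVR mortality, while subjects enrol up to two years after the procedure and must pass the renal and potassium exclusions. No figure is given for subjects who cannot be reached.

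**The case against.** A reader might infer that intolerance is bound to be under-counted. The documents do not support that. They give no capture rate, there is no comparator, subjects know what they are taking, and the listed complaints are non-specific. Steps 2 and 3 show that modest false attribution cancels or reverses the loss. This objection stands, and it is why the point speaks of mis-estimation.

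A reader might also infer that all of Aim 1 rests on this call. It does not. Potassium, the drug effect for which the protocol schedules repeat testing, is measured without relying on recall, and so is blood pressure. A subject lost before 8 weeks can still contribute potassium values, and the call itself is meant to establish vital status.

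Three further limits stand. The protocol gives the coordinator a task, not a script, so it cannot be said that a single open question will be asked, or that the subject and not the coordinator will judge cause. The baseline KCCQ-12 measures symptom frequency, so some pre-drug symptom data exist, though not for the full section 7 list. The draws take place at local sites with no stated study-staff contact, so asking about symptoms at those times would mean new calls. Unscheduled reporting is not described, but it is not ruled out either.

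Finally, in a feasibility registry of 25 the illustrated difference is about two subjects, and the intervals for 3/25 and 5/25 overlap heavily. That limits how much weight the rate can bear. It is no reason to leave avoidable bias in it when the main remedy uses contacts that already exist.

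**Conclusion.** The point holds for symptomatic reactions, which are one part of tolerability. As planned, they are actively sought once, at 8 weeks and as drug reactions, with no baseline beyond the KCCQ-12 and no symptom data from subjects who have died or cannot be reached. The resulting proportion could be too low or too high.

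Its size cannot be fixed from the documents. On the assumptions used, a true 20% would be recorded as 10% to 16% through missed reactions alone, with false attribution pulling the other way. The potassium and blood pressure data are unaffected. This is a cheap improvement worth making, not a fault that invalidates the registry.

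**What to change.** 1. At the 8-week call, use a fixed checklist of the section 7 reactions. Record every event whatever its suspected cause, with onset, and enter the causality judgement separately. Record whether, when and why the drug was stopped.
2. Go through the same checklist at the consent contact, as a baseline.
3. For subjects who died or cannot be reached, take events from the VA record. Add a SAP line reporting the number with a reaction over all who took at least one dose, with an exact 95% CI.

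Optional: a short call at about the time of each post-baseline draw. This is the part that best addresses forgotten early symptoms. It means new contacts, up to 2 × 25 = 50.

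The cost of items 1 to 3 is a one-page checklist and some record review, with no added contact. The reported reaction rate may be higher. The SAP is written in the past tense; if follow-up is already complete, item 3 can still be done, and the single 8-week enquiry should be stated as a limitation beside the rate.
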